## **3. Materials and methods**

### *3.1. Study design*

This was a randomized, single-blind, crossover clinical trial conducted on 2 separate days, with a 1-week washout period between each study day [8]. All participants were randomly submitted to two different test meals with the following similar glycemic index (GI) and different food insulin index (FII) amounts: a low GI and low FII (LGI-LII) content, and a low GI and high FII content (LGI-HII). The order of the test meals was determined by using a computer-generated randomization sequence before recruitment. Test meals were served as a breakfast after 12-hours fasting and participants were asked to consume the meal in full, within 15 min. Venous blood samples were collected just before breakfast (t=0 min) and at time points 15, 30, 45, 60, 90, 120, 180 and 240 min after the meal [9]. Visual analogue scale (VAS) ratings were measured at the same time points, and 4 h after the breakfast, an *ad libitum* buffet-style lunch was served to each participant [10]. The primary outcomes were postprandial responses of serum glucose, insulin and C-peptide. Subjective appetite assessment were the secondary outcomes. The study design was summarized in Figure 1.

This study was conducted according to the guidelines laid down in the Declaration of Helsinki. The Clinical Research Ethics Committee of the Erciyes University approved the protocol (2015/451) on 2 October 2015, and all participants gave written informed consent.

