### *3.2. Participants*

Twenty two obese adolescents with IR who attended the outpatient clinic of the Pediatric Endocrinology, at the Child Hospital of Erciyes University, Kayseri, Turkey were selected on the basis of the following criteria: aged 12-18 years, age- and sex-specific body mass index (BMI)  $\geq$ 95th percentile of the growth-reference data, new diagnosis and not receiving any treatment, and HOMA-IR  $>$ 3.16. Exclusion criteria included hypertension, cardiovascular

disease, diabetes mellitus or any other significant metabolic, endocrine or gastrointestinal disease, use of tobacco or alcohol, taking any medications, and having difficulties for physical activity.

[figure not shown]

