### *3.3. Clinical evaluation*

All participants underwent a detailed physical examination by the pediatric endocrinologist before included in the study. Obesity was defined according to the BMI (weight in kg/height in m^2)  $\geq$ 95th percentile of the WHO 2007 growth-reference for 5-19 years [11,12]. IR was assessed through Homeostatic Model Assessment for IR (HOMA-IR) which is a valid tool for evaluating IR in children and adolescents [13]. This index was calculated as follows: HOMA-IR = [fasting insulin level ( $\mu$ U/mL)  $\times$  fasting glucose level (mmol/L)] / 22.5 [14]. HOMA-IR >3.16 was used as a threshold for IR [15]. Furthermore, pubertal maturation was determined using Tanner-Marshall descriptive standards by the pediatric endocrinologist [16,17]. Systolic blood pressure (SBP) and diastolic blood pressure (DBP) were measured by aneroid sphygmomanometer in the sitting position after 10 min of rest [18].

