### 3.6. Study protocol

At the first visit, clinical, nutritional and physical activity evaluations were performed. Visits 2 and 3 were the test days. Participants received each test meal in a randomly assigned order on two different mornings separated by a washout period of 1-week when they were asked to maintain their usual diet and physical activity [27]. On the day before each test meal, participants were instructed to eat a standard evening meal at 20:00 h and to refrain from eating and/or drinking (except for water) and/or doing any physical activity beyond that of their typical daily activities [28]. Moreover, female participants were tested within the follicular phase of their menstrual cycle (3–10 d after onset of menses) to avoid any effect of menstrual cycle phase on appetite [29-31].

On the each testing day, participants arrived in the testing room at 08.00 h following a 12-h fast and were asked by the dietitian to record their 24-h food and beverage consumption. Participants' body weight, height, body composition and baseline appetite were measured before eating the test meal [8]. Also, a catheter was introduced in an antecubital vein by a registered nurse and a first blood sample was immediately drawn for baseline measurements (time zero) [32]. At 08:30 h participants received the test meal blinded to its nutritional characteristics and were asked to consume within 15 min [9,33]. During the postprandial period, participants remained at rest in the testing room and blood samples were obtained at time points 15, 30, 45, 60, 90, 120, 180, and 240 min [9]. Appetite scale was applied at the same time points [10]. Moreover, participants were asked to assess the organoleptic characteristics (visual appeal, smell, taste, aftertaste and palatability) of test meal by VAS at 15 min (immediately after consuming test meal) [34]. No food or drink other than water was allowed following consumption of the test meal until the *ad libitum* lunch. Water was available *ad libitum* throughout the first trial; however, the volume consumed was measured and the participants drank the same volume during the second trial [35,36]. Participants were permitted to watch movies, read, or play with electronic devices (laptop computer, mobile phone etc.) or undertake other similar sedentary activities throughout each study day but were not allowed to sleep [10,28,37].

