## 4. Statistical Analysis Plan

### 4.1. Sample size and power analysis

Preliminary study was carried out to determine a sample size, and power analysis was conducted by using PASS 11 (power analysis statistical system). A power-based sample size calculation revealed that 16 participants were needed to provide 80% power to detect 5% difference between groups in areas under the curve (AUC) assessed after consumption test meals with similar GI and different FII amounts in obese adolescents with IR. It was decided to complete the study with 20 participants considering 25% losses. However, this study was concluded with 15 participants although 22 participants were recruited. Two enrolled participant declined to eat second test breakfast after consuming first test breakfast. One participant with the IPAQ score  $>1.2$  was excluded from the study because of a decision about including only sedentary participants defined as scoring  $\leq 1.2$  on the IPAQ due to a possible effect of physical activity level on postprandial metabolic response [35]. Moreover, two participant at Tanner stage 3 or 4 were excluded due to a decision about including only participants completed pubertal maturation at Tanner stage 5 for the purpose of minimizing a possible effect of puberty on postprandial metabolic response since hormonal regulation may vary in each pubertal stages [7]. Finally, two participant were not included to the analysis of data because of hemolysis in their blood samples at some time points, leaving a total of 15 participants that were assessed for the main outcomes. When power analysis was repeated, that sample size had 81.2% power to detect differences in primary outcomes among the test meals at alpha level of 0.05.

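### Three recruited participants were removed by activity and Tanner rules missing from the eligibility list, and two more were left out for haemolysis, which cannot affect appetite ratings or lunch intake

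*Combined protocol and SAP*

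**What the plan says.** **Eligibility.** Section 3.2 says that the 22 participants "were selected on the basis of the following criteria: aged 12-18 years", followed by BMI at or above the 95th percentile, a new untreated diagnosis and HOMA-IR above 3.16. Its exclusions cover certain diseases, tobacco, alcohol, medication and difficulty with physical activity. It sets no Tanner stage and no IPAQ limit.

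**Losses.** Section 4.1 goes from 22 recruited to 15:
- Two declined the second breakfast.
- One, with an IPAQ score above 1.2, was "excluded from the study because of a decision about including only sedentary participants".
- Of pubertal stage it says: "two participant at Tanner stage 3 or 4 were excluded due to a decision about including only participants completed pubertal maturation".
- Of haemolysis it says: "two participant were not included to the analysis of data because of hemolysis in their blood samples at some time points".
- The number that results from these losses is described as follows: "leaving a total of 15 participants that were assessed for the main outcomes".

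**Outcomes.** Section 3.1 states: "The primary outcomes were postprandial responses of serum glucose, insulin and C-peptide". Subjective appetite is secondary. Section 3.9 records appetite on paper visual analogue scales, and Section 3.6 obtains lunch intake by weighing food before and after the meal.

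**Analysis.** Section 4.2 compares AUCs with a two-sided paired t test. It defines no analysis population and no rule for a missing time point.

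**The concern.** There are two separate issues.

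First, three people who were among those selected under Section 3.2 were removed under rules that Section 3.2 does not contain. The objective in Section 2 refers to obese adolescents with insulin resistance in general. The results come from the sedentary, Tanner-5 part of that group. At stake is generalisability: a conclusion worded like the objective would cover people the analysis left out.

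Second, haemolysis spoils a blood sample. It does not touch a mark on a paper scale or the weight of a plate. Section 4.1 leaves the two affected participants out of the data analysis without qualification and says the study ended with 15. If that applies to every outcome, two participants' usable appetite and lunch data were lost for no stated reason, in a trial that finished one short of its calculated 16.

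**Working it through.** **1. Participant flow (Section 4.1).** 22 − 2 (declined second meal) − 1 (IPAQ) − 2 (Tanner) − 2 (haemolysis) = 15. The plan's figure is reproduced exactly. The unlisted rules account for 3/22 = 13.6% of those recruited, and all losses together for 7/22 = 31.8%, against the 25% allowed for.

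**2. Eligibility set against exclusions.** Section 3.2 admits ages 12 to 18 without a pubertal limit, whereas Section 4.1 requires Tanner stage 5. The only activity item in Section 3.2 excludes people who have difficulty being active, whereas Section 4.1 excludes someone for being too active. These are different rules, so the two sections describe different populations.

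**3. Scale of the activity cut-off.** Section 3.5 scores the IPAQ in MET-minutes per week. MET-minutes are METs times minutes, so 1.2 on that scale would be at most about one minute a week at 1 MET or more. The cut-off of 1.2 in Section 4.1 must belong to some other scale, which is not stated.

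**4. What haemolysis removes.** Section 3.8 gives 9 samples per test day, hence 9 × 2 = 18 per participant. The plan says only some time points were affected and gives no number. No appetite rating or lunch weight depends on a blood sample.

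**5. Size for appetite and lunch.** With both haemolysis cases kept, n = 22 − 2 − 1 − 2 = 17. The 95% half-width for a mean paired difference, in units of the SD of differences, is t(0.975, n−1)/√n:
- n = 15: 2.145/√15 = 0.554
- n = 17: 2.120/√17 = 0.514

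The reduction is 1 − 0.514/0.554 = 7.2%, if the SD of differences stays the same.

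**6. Size for blood outcomes.** The plan gives no SD, so the standardised effect has to be back-solved from its power statements (two-sided paired t test, alpha 0.05):

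| Basis for the effect | Effect (SD of differences) | Power, n = 15 | Power, n = 17 |
|---|---|---|---|
| 80% exactly at n = 16 | 0.749 | 77.0% | 82.6% |
| Upper limit at which 16 is still the smallest n reaching 80% | 0.778 | 80.0% | 85.3% |
| Stated 81.2% at n = 15 | 0.790 | 81.2% | 86.4% |

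The n = 17 column would need 17 complete blood profiles, which do not exist. What the two partial profiles add depends on how many samples were spoiled, which ones, and the correlation between samples. None of this is in the documents. Under assumed variances, three of 18 samples missing at random in each of the two gives an effective n of about 16.6 to 17.0. If the three are the last ones of a single test day, it is about 16.05 to 16.88. A mixed model using the partial profiles was simulated under two assumed serial-correlation patterns without a participant-by-day effect. Its type I error was 3.5% and 3.6% rather than 5%. At that size its power is roughly 77.5% to 78.0%, against 77.0% for the existing t test. The gain therefore ranges from almost nothing to a few points, and the documents cannot narrow it.

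**The case against.** The strongest reply is that nothing is hidden. Section 4.1 gives each rule, its count, its scientific reason and a citation, and protocol and SAP are one document, so a reader can work out who was analysed. That stands, and it is why the point is minor. It does not make Sections 3.2 and 4.1 agree, or make the objective fit the sample.

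The three may also have been removed before any test meal. Section 3.3 says "All participants underwent a detailed physical examination by the pediatric endocrinologist before included in the study", and Section 3.6 says "At the first visit, clinical, nutritional and physical activity evaluations were performed", with test days at visits 2 and 3. This is a natural reading, and under it no analysis changes, only wording. The design figure is not available to settle it.

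The phrase about main outcomes may refer only to the blood measures that Section 3.1 calls primary, in which case appetite may already have been analysed with 17. That is possible, but the plan does not say so. Lunch intake is named as neither a primary nor a secondary outcome in Section 3.1, so its loss would weigh less.

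Three stronger readings are tempting, and the documents support none of them:
- **The rules were chosen after seeing results.** The text does not say when the decisions were taken or what was known then. Activity and pubertal stage are participant characteristics, and in a crossover removing a person removes both meals alike, so no within-person bias follows.
- **Usable test-day data from the three were discarded.** The text does not say that they ate a test meal.
- **Keeping the two haemolysis cases restores a definite amount of power.** The back-solved effect belongs to the AUC planning calculation and does not carry over to appetite or lunch. For blood outcomes the gain rests on assumptions.

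**Conclusion.** The concern holds as a minor one. The counts are certain: three of 22 were removed by rules absent from Section 3.2, and two of 22 were left out for haemolysis at some time points. The analysed population is sedentary and Tanner stage 5, which is narrower than the objective.

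Whether appetite and lunch were analysed with 15 or 17 is not settled by the text, although 15 is the plain reading. If it was 15, keeping both participants narrows those intervals by about 7%, assuming the same SD of differences and usable appetite and lunch data from both test days for the two. Confidence is high for the counts and low for any power gain.

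**What to change.** 1. **Haemolysis.** Keep both participants in the appetite and lunch analyses (n = 17). State n for each outcome and how many samples were spoiled. Keep the paired AUC t test on complete profiles for the blood outcomes. An added analysis using the valid samples of the two is optional. It would have to be labelled post hoc, with its missing-at-random assumption stated.
2. **Population.** Reconcile Section 3.2 with Section 4.1. If the three were removed before testing, say so, list both rules under eligibility, and limit the conclusion to sedentary, Tanner-5 obese adolescents with insulin resistance. If they have data from both test days, analyse everyone who meets Section 3.2 and report the sedentary, Tanner-5 subset as a sensitivity analysis.
3. **Activity cut-off.** State the scale on which 1.2 is measured and how it relates to the scoring in Section 3.5.

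The cost is revised wording and a re-run on existing data for two participants, with a further re-run only if test-day data exist for the three. The downsides are a more heterogeneous sample if the three are added, and that any change made now is post hoc because the trial has ended.

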## 4.2. Data analysis

Statistical analysis was performed using the Statistical Package for the Social Sciences (version 22.0; IBM SPSS Statistics) software. Data were expressed as the number (n) and percentage (%) for categorical variables, and means  $\pm$  SDs, medians (25th–75th percentiles) for continuous variables. Normality was assessed using the histogram and normal Q-Q plots, and also Shapiro-Wilk test. Furthermore, continuous variables were examined for skewness and kurtosis, and log-transformed before analysis and reported back-transformed geometric means (G)  $\pm$  standard error (S.E) when required [43]. Differences between groups were tested using t-tests. Categorical variables were compared by the chi-square tests. Wilcoxon signed rank tests were used for continuous variables without normal distributions. Postprandial responses for metabolic parameters and appetite sensations were quantified as area under the curve (AUC) calculated according to the trapezoidal rule [8,33]. As an estimate of glucose-adjusted insulin response, the index of insulin response to glucose was calculated as an insulin/glucose ratio by using serum glucose and insulin levels at time points [9]. A Student's 2-tailed t test for paired data was applied to determine statistical differences between AUCs. In addition, between-group comparisons were analyzed by using 2-factor (diet x time) repeated-measures analysis of variance (ANOVA), and Bonferroni post hoc tests were applied to significant group x time interactions. Baseline values for each variable were compared between groups by using paired t tests. In the event of a significant t statistic, baseline values were used as a covariate in the 2-factor repeated-measures ANOVA. For all statistical analyses, p values less than 0.05 were considered to have statistical significance [44].

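### The two-visit crossover is analysed without a visit (period) term, so any common visit effect inflates the error and, with 15 participants, partly enters the meal estimate

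*Combined protocol and SAP*

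**What the plan says.** Section 3.1 describes a randomised two-meal crossover on two days one week apart. On allocation it says: "The order of the test meals was determined by using a computer-generated randomization sequence before recruitment". No ratio, blocking or number per order is given. On outcomes: "The primary outcomes were postprandial responses of serum glucose, insulin and C-peptide". Appetite ratings are secondary.

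Section 4.2 lists the meal comparisons:

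- AUCs: "2-tailed t test for paired data was applied to determine statistical differences between AUCs".
- Non-normal variables: "Wilcoxon signed rank tests were used for continuous variables without normal distributions".
- Time courses: "between-group comparisons were analyzed by using 2-factor (diet x time) repeated-measures analysis of variance (ANOVA"). Time here is the sampling time after the meal (0 to 240 min), not the visit.
- Baseline: "In the event of a significant t statistic, baseline values were used as a covariate in the 2-factor repeated-measures ANOVA".

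No visit, period or order term appears in any of these.

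Section 4.1 accounts for the losses from 22 recruited, "leaving a total of 15 participants that were assessed for the main outcomes". It then says that "that sample size had 81.2% power to detect differences in primary outcomes among the test meals", at alpha 0.05.

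**The concern.** In a two-visit crossover, each within-person meal difference contains the visit difference, with a plus sign in one order and a minus sign in the other. Leaving visit out has two effects.

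1. **Precision.** The plus and minus shifts spread the differences out. The error variance grows and the interval widens. This happens even when the orders are perfectly balanced.
2. **The estimate in this sample.** With unequal orders the shifts do not cancel, so part of the visit effect is read as a meal effect.

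A visit effect is plausible but not shown. Section 3.6 has water freely available at the first test and fixed to that volume at the second. A girl tested twice in one cycle is always later in it at the second test. The two rules on cycle window and one-week gap can both be met (days 3 and 10), and no breach is reported. The first four-hour session with a cannula is also new to the participant, and the second is not.

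The baseline covariate is only a partial safeguard. It is used only when baselines differ significantly between meals, and it does not reach the AUC t test.

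**Working it through.** **Inputs from the documents.** 22 recruited; losses of 2, 1, 2 and 2; 15 analysed; two-sided alpha 0.05; stated power 81.2% at 15 and 80% at 16 (section 4.1).

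**Assumed.** Visit effect k of 0.25, 0.5 or 1.0, in units of the SD of the within-person meal difference. Splits from 8:7 to 11:4.

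**Number analysed.** 22 − 2 − 1 − 2 − 2 = 15, as stated. It is odd, so 8:7 is the most even split possible.

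**The plan's power figure.** No SD is given, so it can only be solved backwards, assuming a paired t test. Power of 81.2% at n = 15 needs an effect of 0.790 SD. Power of 80% at n = 16 needs 0.749 SD, which at n = 15 gives 77.0%. If 16 is the smallest number that reaches 80%, power at 15 cannot exceed 80.0%. So the 81.2% uses inputs other than those behind the 16.

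**Share of the visit effect in the meal estimate.** The meal difference shifts by +k in one order (n1 people) and −k in the other (n2), so the paired mean shifts by k(n1 − n2)/15.

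**Error variance.** With SD 1 within each order, the expected variance of the differences is 1 + c k², where c = 4 n1 n2/(15 × 14). The standard error is multiplied by √(1 + c k²). At 8:7, c = 4 × 56/210 = 1.067, so the factors are √1.067 = 1.033 (k = 0.25), √1.267 = 1.125 (k = 0.5) and √2.067 = 1.438 (k = 1.0). A balanced 8:8 gives c = 4 × 64/(16 × 15) = 1.067, the same value, so the precision loss does not come from the odd number.

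**Cost of the term when there is no visit effect.** Interval width ratio = t(13 df)/t(14 df) × √(15(1/n1 + 1/n2)/4). At 8:7 this is 2.160/2.145 × 1.002 = 1.010. The term pays for itself once k exceeds √((width² − 1)/c). Power with the term comes from the noncentral t with 13 df at 0.790 SD.

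| Split | Share of visit effect in meal estimate | SE factor, k = 0.25 / 0.5 / 1.0, no term | Width ratio with term, k = 0 | Break-even k | Power with term |
|---|---|---|---|---|---|
| 8:7 | 0.067 | 1.03 / 1.13 / 1.44 | 1.010 | 0.13 | 80.6% |
| 9:6 | 0.20 | 1.03 / 1.12 / 1.42 | 1.028 | 0.24 | 79.1% |
| 10:5 | 0.33 | 1.03 / 1.11 / 1.40 | 1.068 | 0.39 | 76.0% |
| 11:4 | 0.47 | 1.03 / 1.10 / 1.36 | 1.139 | 0.60 | 70.7% |

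**False-positive rate without the term** (simulated, 400,000 trials per case):

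| Split | k = 0.5 | k = 1.0 |
|---|---|---|
| 8:7 | 3.1% | 0.8% |
| 9:6 | 4.0% | 2.3% |
| 10:5 | 6.2% | 6.8% |
| 11:4 | 9.9% | 17.1% |

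**How likely is each split?** If 11:11 were assigned and the seven losses were random, 8:7 has probability 2 × C(11,8) × C(11,7)/C(22,15) = 64%, 9:6 has 30%, and 10:5 or worse has 6%. Under simple randomisation the figures are 39% (8:7), 31% (9:6), 18% (10:5) and 12% (11:4 or worse).

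**The case against.** The strongest reply is that validity is sound at the likely splits. Order was randomised, so the meal comparison is unbiased over repeated randomisations, and at 8:7 and 9:6 the unadjusted test is conservative. This stands, and it makes the point mainly one of efficiency.

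The mechanisms are also weak. Matching water volume equalises intake, and the cycle window is itself a control. The number of girls is not given. Section 3.6 standardises the evening meal, fast, clock times and rest. All of this makes a large visit effect less likely; an effect of 1.0 SD would exceed the 0.790 SD meal effect behind the power figure.

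A reader might infer that the trial has clearly less than its stated 81.2% power. The documents do not support that. Section 4.1 says the power analysis was repeated once 15 participants remained. If it used the observed SD of the paired differences, that SD already contains any visit variance, and subtracting it again would count it twice. A reader might also infer that the odd number causes the precision loss; 8:8 gives the same variance coefficient as 8:7.

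The term is not free if the split is very uneven. At 11:4 with no visit effect it costs more than 10 points of power.

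Finally, the documents describe a finished study, so replacing the stated tests now would be a post hoc change. That bears on how the adjusted analysis is presented. It is not a reason to leave it out.

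**Conclusion.** The omission is real and applies to all three methods in section 4.2. A visit effect common to all participants would widen the interval for the glucose, insulin, C-peptide and appetite AUCs: by about 3% at 0.25 SD, 13% at 0.5 SD and 44% at 1.0 SD with an 8:7 split. In this one sample, between 0.067 (8:7) and 0.47 (11:4) of that effect would also be read as a meal difference.

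The size rests on two quantities that the documents do not give: the visit effect, which may be zero, and the split. An inflated false-positive rate arises only at 10:5 or worse, and since the split is unreported, a reader can neither assert nor exclude it. No specific loss from the stated 81.2% can be claimed. This is a cheap improvement, not a flaw that invalidates the meal comparison.

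**What to change.** For the primary and appetite AUCs:

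1. Take each participant's visit 1 minus visit 2 difference and compare it between the two meal orders with a two-sample t test. Half the difference in means is the meal effect, free of a common visit effect. For non-normal outcomes, use a rank-sum test on the same differences in place of the signed-rank test.
2. In the diet x time ANOVA, add meal order as a between-subject factor. Its interaction with diet absorbs the visit effect.
3. Report how many analysed participants had each order.

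If the unadjusted tests have already been run, show this beside them, labelled as a period-adjusted analysis. It would also help to report girls' cycle day at each test, because the term fully removes a girls-only shift only if affected girls form the same share of both orders.

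**Cost.** One degree of freedom and no new data, since the order comes from the randomisation sequence. With no visit effect, the interval is 1% wider at 8:7, 3% at 9:6, 7% at 10:5 and 14% at 11:4. The matching power figures, from 80.6% down to 70.7%, take 81.2% as the power of the paired t test.

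### A chance-driven baseline t-test decides whether the diet-by-time ANOVA is baseline-adjusted, while the AUC t-test has no stated baseline covariate; one handling should be fixed for both

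*Combined protocol and SAP*

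**What the plan says.** Section 4.2 of the combined protocol and SAP gives two analyses of the postprandial responses.

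- **AUC comparison.** Responses are "quantified as area under the curve (AUC) calculated according to the trapezoidal rule". Then: "A Student's 2-tailed t test for paired data was applied to determine statistical differences between AUCs". No baseline covariate is stated, and the section does not say whether the AUC is total or incremental.
- **Diet-by-time model.** "In addition, between-group comparisons were analyzed by using 2-factor (diet x time) repeated-measures analysis of variance (ANOVA").

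Baseline is handled by a pre-test: "Baseline values for each variable were compared between groups by using paired t tests". The result decides the model: "In the event of a significant t statistic, baseline values were used as a covariate in the 2-factor repeated-measures ANOVA". The significance level is 0.05 throughout.

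Section 3.1 randomises meal order with a one-week washout, takes t=0 measurements on both test days, and names the glucose, insulin and C-peptide responses as primary outcomes. Section 4.1 sizes the study on AUC: "16 participants were needed to provide 80% power to detect 5% difference between groups in areas under the curve (AUC"). It also reports that "this study was concluded with 15 participants". Read together, these sections point to the AUC t-test as the main analysis and the ANOVA as a supplement, but no sentence labels either one primary.

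**The concern.** Baseline adjustment is worthwhile when baseline predicts response. A significance test of the baseline difference does not measure that. With meal order randomised and no carryover, the null hypothesis of the baseline test is true by design, so its result is noise: the rule adjusts in a random 5% or so of cases per variable and leaves the rest unadjusted.

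The rule also applies to only one of the two analyses. When it fires, the ANOVA is adjusted and the AUC t-test of the same outcome is not. A reader can then be shown two answers that differ partly because of baseline handling, with no stated rule on which one governs.

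**Working it through.** **Inputs from the documents.** Analysed n = 15 and planned n = 16 with 80% power (section 4.1); alpha = 0.05 (section 4.2); three primary outcomes and sampling at 0, 15, 30, 45, 60, 90, 120, 180 and 240 min (section 3.1). **Assumed:** rho, the correlation between the within-person t=0 difference and the within-person AUC difference. The documents do not give it, so a range is shown.

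**1. The plan's sizing figure.** No SD is stated, so 16 cannot be reproduced outright. An exact two-sided paired t calculation gives 80% at n=16 for a standardised difference d = 0.7495. That corresponds to an SD of within-person differences of 5% / 0.7495 = 6.67% of AUC. The same d gives 77.0% at n=15. Section 4.1 instead states that "that sample size had 81.2% power to detect differences in primary outcomes among the test meals at alpha level of 0.05", which needs d = 0.790; that is a separate matter and nothing below depends on it. I use d = 0.7495 as the reference effect.

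**2. How often the pre-test fires.** 5% per variable by design. For at least one of the three primary outcomes: 1 − 0.95³ = 14.3% if independent, and at most 3 × 5% = 15% under any dependence.

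**3. What firing does to agreement.** Simulated within-person differences at the nine times, n=15, five assumed covariances (rho 0.26 to 0.68, total AUC). The comparison is the AUC t-test against the ANOVA diet main effect, taken as the equal-weight mean of 15–240 min. Percentage of trials in which the two tests disagree:

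| | Plan's rule | Neither adjusted | Both adjusted |
|---|---|---|---|
| Null, pre-test fired | 9–28 | 5–10 | 2–4 |
| Null, all trials | 2.8–3.7 | 1.7–3.5 | 2.3–3.6 |
| d=0.7495, pre-test fired | 24–36 | 4–10 | 4–13 |
| d=0.7495, all trials | 6.7–10.7 | 5.1–10.1 | 2.3–10.0 |

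Over all null trials the rule adds about 0.2–1.1 points compared with adjusting neither, and 0.1–0.6 compared with adjusting both. Firing and disagreeing together occurs in 0.5–1.4% of null trials per outcome. The diet-by-time interaction was not simulated, because the plan does not state the time levels or how the covariate enters.

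**4. The unadjusted AUC test after a chance imbalance.** Simulated pairs (t=0 difference, AUC difference), bivariate normal, n=15. Unadjusted: one-sample t on the AUC difference, 14 df. Adjusted: intercept from regressing the AUC difference on the t=0 difference, 13 df. The pre-test fires when its |t| > 2.145. The AUC mean is then displaced by at least roughly rho × 2.145 standard errors, for example 1.07 at rho 0.5. Type I error of the AUC test:

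| rho | All trials, unadjusted | Fired, unadjusted | Fired, adjusted |
|---|---|---|---|
| 0 | 5.0% | 4.9% | about 5% |
| 0.3 | 5.0% | 9.2% | about 5% |
| 0.5 | 5.0% | 16.5% | about 5% |
| 0.7 | 5.0% | 30.1% | about 5% |

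The sign of rho does not matter, since reversing the sign of the baseline difference leaves both tests unchanged.

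**5. Average power if the AUC test were always adjusted,** d=0.7495, against 77.0% unadjusted: 73.4% (rho 0), 75.1% (0.2), 77.2% (0.3), 84.6% (0.5), 94.9% (0.7).

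**6. Total or incremental AUC.** Net incremental AUC = total AUC − 240 × (t=0 value). Regressing either on the t=0 difference gives the same intercept and residuals; only the slope shifts, by 240. So the adjusted tests are identical on the untransformed scale. Unadjusted, they disagree in about 9.3% of null trials.

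**The case against.** The strongest defence is that the rule hardly matters. It touches only the supplementary ANOVA, fires rarely, and most disagreement between the two tests arises because they weight time points differently: trapezoid weights put 56% of the AUC on 120–240 min, while the ANOVA main effect weights times equally. That stands, and it sets the severity.

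Four stronger readings are tempting, and the documents do not support them.

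- *The rule inflates false positives.* It does not. The AUC test stays at 5.0% overall. Applying the conditional rule to a single summary difference per person, as a stand-in for the ANOVA, gives 4.9%, 4.8%, 4.4% and 3.7% at rho 0, 0.3, 0.5 and 0.7.
- *The 9–30% conditional error is caused by the rule.* It belongs to any unadjusted test after a chance imbalance and would remain if the pre-test were simply deleted. It is an argument for adjusting, not evidence against the quoted sentence.
- *Baseline plays no part in the AUC test.* Only the absence of a stated covariate is documented. A total AUC includes t=0 as its first point, with weight 7.5/240 = 3.1%; an incremental AUC subtracts it. The sources cited for the AUC method cannot be consulted here. The agreement figures in step 3 are for total AUC; under the same covariances net incremental AUC has rho of −0.66 to −0.88.
- *The rule costs the ANOVA a known amount of power.* The power figures above are for the AUC test, which the rule never adjusts. No ANOVA power was computed.

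It is also fair that always adjusting is a choice and not a free gain: at low rho it loses power, and rho is unknown.

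**Conclusion.** The point holds at low to moderate severity. The plan states a data-dependent rule whose trigger, under randomised order, carries no information about whether adjustment is useful, and it applies the rule to one of two analyses of the same outcome. The direct cost is an occasional, avoidable inconsistency: about a point or less of extra disagreement over all null trials, and at d=0.7495 a shift in the range from 5.1–10.1% to 6.7–10.7% (0.6 to 1.6 points at its ends). The larger statistical issue, which exists with or without the rule, is that an unadjusted AUC comparison is unreliable in those trials where baselines happen to differ. The undefined AUC adds to this.

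This rests on no carryover across the one-week washout, on the exclusions described in section 4.1 not having disturbed the randomised comparison, on approximate normality of the differences, and on assumed values of rho.

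**What to change.** Delete the baseline significance test. Use one baseline handling, chosen without a test, in both the AUC comparison and the diet-by-time model.

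- **Suggested:** for outcomes with a t=0 value (so not palatability or lunch intake), always include the within-person t=0 difference as a covariate in the AUC comparison. In the meal-by-time model, use 15–240 min as responses and t=0 as covariate.
- **Simpler alternative:** no baseline covariate in either analysis. This removes the inconsistency at no cost but keeps the conditional error in step 4.

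Name the primary analysis and state whether AUC is total or incremental. With the suggested adjustment, that distinction no longer affects the test on the untransformed scale with the linear model. It still matters after log transformation or with Wilcoxon tests, both of which section 4.2 allows.

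**Cost.** No new data are needed, because t=0 was measured on both test days. Section 4.1 reports the study as concluded, so the re-analysis should be labelled post hoc and shown beside the result of the plan as written. The covariate uses one degree of freedom. Average power changes by 73.4 − 77.0 = −3.6 points if rho is 0, breaks even near 0.3, and rises to about 85% at 0.5 and 95% at 0.7.
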